6.7.2 Prohibited therapies from baseline to the end of the treatment period

Use of any therapy that would exclude the subject from participation in the trial (as specified in Section 5.3) is also prohibited during the treatment period, which includes therapies in the following categories:

- Start of new or change of existing systemic treatment for CKD-aP, including but not limited to antihistamines, corticosteroids, opioids, GABA analogues, or kappa opioid receptor agonists (but stable systemic CKD-aP treatment can be continued).
- Any topical treatment on CKD-aP areas, including but not limited to emollients, antihistamines, and corticosteroids

- Therapeutic anticoagulation treatment for subjects who have skin biopsies performed (heparin administered in association with dialysis is allowed but in such cases skin biopsies must not be performed on a dialysis day)
- Any light therapy for CKD-aP, including but not limited to UV-B
- Start of new or change of existing non-biologic systemic immunosuppressive treatment, including but not limited to corticosteroids, cyclosporin and tacrolimus
- Start of new or change of existing biologic systemic treatment, including but not limited to etanercept, adalimumab, alefacept, infliximab, and ustekinumab

If a prohibited therapy is used during the trial, treatment with the IMP shall not automatically be discontinued. After consultation with the sponsor's or designee's Medical Monitor, the investigator shall use his/her judgement to decide if (in the following prioritized order) 1) The prohibited therapy can safely be stopped; 2) the prohibited therapy cannot safely be stopped but the IMP treatment can safely continue alongside the prohibited therapy; or 3) the prohibited therapy cannot safely be stopped and the IMP treatment cannot safely continue alongside the prohibited therapy. The event must be reported as a protocol deviation.

6.8 Therapies not listed are allowed. Treatment compliance and drug accountability

Records of trial product used, and dosages administered will be kept during the trial. The trial monitor will note product accountability during site visits and at the completion of the trial. Subjects will be asked to return all used and unused tubes in the outer box at each visit to ensure drug accountability. All returned tubes that had been dispensed to a subject and have broken seals will be weighed to determine the amount of the IMP.

At all on-treatment visits, the subject will be asked if he/she has used the trial medication as prescribed and to indicate the CKD-aP treatment area size. Any degree and nature of noncompliance will be specified. In addition, subjects will be asked to complete a dosing diary during the treatment period as a measure of treatment compliance. Subjects who are consistently noncompliant will be counselled.

7.0 VISIT SCHEDULE AND ASSESSMENTS

7.1 Visit schedule

The schedule of assessments (SoA) is provided in Table 3.

The informed consent process must be completed before any other assessment or procedure. The following order of assessments must always be adhered to:

- Patient Reported Outcomes should be assessed before all other clinical assessments or procedures.
- Skin tape stripping and skin biopsies of CKD-aP target areas must be taken after imaging and CTA of CKD-aP target areas.

On-site visit days should preferably be on the same weekday throughout the trial for subjects on dialysis. On-site visits should be aligned with dialysis visits to the extent possible to avoid unnecessary travelling for subjects on dialysis.

Table 3:Visit Schedule

Trial Period	Screening Period	Treatment Period				FU period ¹				
Visit Number ²	1 (Screening)	2 (Baseline)	3	4	5	6	7	8	9 (EoT) ³	10 (FU)
Trial Week		0	1	2	4	6	8	10	12	14
Days from Baseline (Visit 2)	-28 to -1	0	7	14	28	42	56	70	84	
Visit Window	NA	NA	±1	±2	±4	±2	±4	±2	±4	±2
In-clinic or Phone Visits ⁴	In-Clinic	In-Clinic	In- Clinic	Phone	In- Clinic	Phone	In- Clinic	Phone	In- Clinic	In- Clinic
Informed Consent ⁵	Х									
Eligibility Assessment	Х	Х								
Demographics	Х									
CKD History	Х									
Medical History	Х									
CKD-aP Treatment History	Х									
Worst Itch NRS (WI-NRS) – at-home (diary) assessments ⁶		Х	Х		Х		Х		Х	
Worst Itch NRS (WI-NRS) – On-site assessment ^{7, 8}	Х	Х	Х		Х		Х		Х	
Sleeploss due to Itch NRS (SI-NRS) ⁸	Х	Х	Х		Х		Х		Х	
Skin Dryness NRS (SD-NRS) ⁸	Х	Х	Х		Х		Х		Х	
Subject's Global Impression of Change (SGIC) ⁸			Х		Х		Х		Х	
Subject's rating of importance of improvement ⁸			Х		Х		Х		Х	
Subject's indication of CKD-aP treatment area size ^{8,9}		Х	Х		Х		Х		X	
5D-Itch ⁸		Х			Х		Х		Х	
Skindex-10 ⁸		Х			Х		Х		Х	
EQ-5D-5L ⁸		Х			Х		Х		Х	
CKD-aP target area identification		Х								
CGA of Skin Appearance	Х	Х	Х		Х		Х		Х	
CTA of Skin Appearance		X	Х		Х		Х		X	
Physical examination ¹⁰	X	X							Х	(X)
Vital signs ¹¹	X	Х			Х		X		Х	(X)

Trial Period	Screening Period			Tr	eatment	t Period				FU period ¹
Visit Number ²	1 (Screening)	2 (Baseline)	3	4	5	6	7	8	9 (EoT) ³	10 (FU)
Trial Week		0	1	2	4	6	8	10	12	14
Days from Baseline (Visit 2)	-28 to -1	0	7	14	28	42	56	70	84	
Visit Window	NA	NA	±1	±2	±4	±2	±4	±2	±4	±2
Single 12-lead ECG		Х			Х				Х	(X)
Pregnancy Testing ¹²	X	Х			Х				Х	(X)
Laboratory Assessments ¹³	X	Х			Х				Х	(X)
Imaging of CKD-aP ¹⁴		Х			Х				Х	
Randomisation		Х								
Diary (Handout)	Х	Х	Х		Х		Х			
Biopsy ¹⁵		Х							Х	
Tape stripping ¹⁶		Х							Х	
Prior & concomitant therapies ¹⁷	Х	Х	Х	Х	Х	Х	Х	Х	Х	Х
Adverse events		Х	Х	Х	Х	Х	Х	Х	Х	Х
Investigational medicinal product (IMP) dispensation		Х			Х		Х			
IMP return, compliance and accountability					Х		Х		Х	
IMP application ¹⁸				_	Х					
Diary (Review)		Х	Х		Х		Х		X	

- 1. Follow-up (FU) visit is only applicable if there are ongoing serious adverse events (SAEs) or related adverse events (AEs) at Week 12. (X) indicates assessments to be performed if judged necessary by the investigator.
- 2. An unscheduled visit can be conducted to perform any of the postbaseline assessments or procedures included in the SoA if deemed necessary by the Investigator.
- 3. In the case of trial withdrawal or treatment discontinuation, all assessments of the Week 12 (End of Treatment [EoT]) visit have to be performed. The end of treatment form must be completed when treatment is discontinued and the end of trial form must be completed at end of the trial or in case of trial withdrawal.
- 4. Phone calls: To remind subjects about diary documentation (in particular once-daily WI-NRS assessments that must be performed for 8 days leading up to each on-site visit [i.e., from day -7 to day 0 where day 0 = next on-site visit day]) and to ask for AEs. Phone visits may be replaced by in-clinic visits where relevant, e.g., in subjects going to the dialysis unit for haemodialysis.
- 5. Informed consent must be signed by both subject and investigator before any trial-related procedures are performed.

Clinical Trial Protocol

Protocol No. MC2-25-C1 Vers.3.0 EU/30-Nov-2022

- 6. At-home (diary) assessments must be performed for 8 days leading up to each visit, i.e., from day -7 to day 0 where day 0 = next on-site visit day.
- 7. The WI-NRS must also be reported by the subject at on-site visits
- 8. At all on-site visits, all patient-reported outcome (PRO) assessments should be completed before all other clinical assessments or procedures.
- 9. The trial staff must estimate the % body surface area treated based on the subject's indication of CKD-aP treatment area size on the CKD-aP treatment area diagram.
- 10. Physical exam: A complete physical examination is required at Screening and Week 12 (EoT or Early Termination) visits. An abbreviated physical examination is required at the Baseline visit (and if judged necessary by the investigator) at the FU visit if the FU visit is applicable.
- 11. Vital signs include blood pressure, heart rate, and body temperature measurement. For subjects on haemodialysis vital signs are to be assessed prior to dialysis. Blood pressure and pulse rate will be taken with the subject in the sitting position with approximately 5 minutes rest prior to measurement.
- 12. Serum pregnancy tests are conducted for women of childbearing potential. At Baseline a urine pregnancy test must also be conducted except for dialysis subjects with anuria.
- 13. For subjects on dialysis, the blood samples must be collected before dialysis.
- 14. Only at selected sites and only for subjects who have provided additional consent. CKD-aP target area selected at Baseline. Images of CKD-aP target area must be taken before tape stripping and skin biopsies.
- 15. Only at selected sites and only for subjects who have provided additional consent. Biopsy: 4 mm skin punch biopsy (optional) is taken from the CKD-aP target area.
- 16. Tape stripping is conducted in all subjects from the CKD-aP target area.
- 17. "Therapies" refers to medications and therapies.
- 18. The first IMP application shall preferably be performed in the clinic under surveillance, and assistance if necessary, of trial staff.

7.2 Demographics and medical history

The following demographic and medical history must be collected in the eCRF:

- Year of birth
- Sex
- Race
- Subject-reported ethnicity
- CKD stage and history, including age of diagnosis, severity, and in subjects on haemodialysis (HD or HDF), information on haemodialysis
- All other current and past medical/surgical conditions within the previous 12 months

7.3 **Prior and concomitant therapies**

Prior or concomitant therapies as defined in Section 6.7 must be recorded in the eCRF at all trial visits. Information regarding the total daily dose, route of administration, start and discontinuation dates, and indication are to be recorded on the subject's eCRF.

7.4 Physical examination

A complete physical examination (i.e., including all organ systems as well as the skin) is required at Screening and Week 12 or (EoT or Early termination). The height and weight can be self-reported. An abbreviated physical examination (i.e., including the skin as a minimum; other organ systems may be included depending on present signs, symptoms or investigation outcomes) is conducted at Baseline. For subjects with SAEs or ongoing related AEs at Week 12, an abbreviated physical examination is also conducted at Week 14 (Follow-up) if judged necessary by the investigator.

Any abnormalities must be assessed as "clinically significant" or "not clinically significant" by the investigator. Abnormalities classified as "clinically significant" must be recorded in the eCRF as AEs except those observed at Screening visit 1, which will be recorded as medical history.

7.5 Vital signs

Vital signs must be recorded in the eCRF. Vital signs (systolic and diastolic blood pressure, heart rate, and body temperature) will be measured at Screening, Baseline, Week 4, Week 8, and Week 12 (EoT or Early Termination) visits. For subjects with ongoing SAEs or related AEs at Week 12, vital signs are also measured at Week 14 (Follow-up) if judged necessary by the investigator. In haemodialysis subjects, vital signs are to be recorded prior to dialysis. Blood pressure and heart rate will be taken with the subject in the sitting position with approximately 5 minutes rest prior to measurement. Body temperature (oral or ear) will also be measured.

Any abnormalities must be assessed as "clinically significant" or "not clinically significant" by the investigator. Abnormalities classified as "clinically significant" must be recorded in the eCRF as AEs except those observed at Screening visit 1, which will be recorded as medical history.

7.6 Electrocardiogram (ECG)

A single 12-lead ECG must be recorded using local equipment at Baseline, Week 4, and Week 12 or Early Termination. For subjects with ongoing SAEs or related AEs at Week 12, a single 12-lead ECG will also be performed at Week 14 (Follow-up) if judged necessary by the investigator. In haemodialysis subjects, ECGs are to be performed preferably prior to dialysis. Interpretation of ECGs will be based on machine read-out and local physician evaluation (cardiologist overread will not be performed).

Any abnormalities must be assessed as "clinically significant" or "not clinically significant" by the investigator. Abnormalities classified as "clinically significant" must be recorded in the eCRF as AEs except those observed at Screening visit 1, which will be recorded as medical history.

7.7 Pregnancy test

Women of childbearing potential will undergo a serum pregnancy test at Screening, Baseline, Week 4, and Week 12 or Early Termination. At Baseline a highly sensitive urine pregnancy test (i.e. with sensitivity down to at least 25 mIU/ml for human chorionic gonadotrophin (hCG)) must also be conducted except in dialysis subjects with anuria. At the investigator's discretion, additional testing for pregnancy may be performed at the FU visit if this visit is applicable.

All pregnancies must be recorded in the eCRF and should be immediately reported to the sponsor or designee and followed through to resolution (i.e., delivery, miscarriage, or abortion). The report should be submitted within the same timelines as an SAE (within 24 hours of knowledge), although a pregnancy per se is not considered an SAE.

7.8 Laboratory assessments

Clinical laboratory specimens will be analysed by a central licensed and accredited laboratory facility according to the laboratory's standard operating procedures.

Any abnormalities must be assessed as "clinically significant" or "not clinically significant" by the investigator. Abnormalities classified as "clinically significant" must be recorded in the eCRF as AEs except those observed at Screening visit 1, which will be recorded as medical history.

7.8.1 Haematology and biochemistry

For all subjects, the following tests will be performed at Screening, Baseline, Week 4, and Week 12 or Early Termination. For subjects with ongoing SAEs or related AEs at Week 12, laboratory tests will also be performed at Week 14 (Follow-up) if judged necessary by the investigator. In patients on dialysis, the blood samples must be collected before dialysis:

- Haematology: haemoglobin, haematocrit, red blood cell (RBC) count, mean corpuscular volume (MCV), and white blood cells (WBC) count (basophils, eosinophils, neutrophils, lymphocytes, and monocytes), including differential count and platelet count
- Serum biochemistry: urea, creatinine, albumin, sodium, potassium, chloride, calcium, phosphate, alkaline phosphatase (ALP), aspartate aminotransferase (AST), and alanine aminotransferase (ALT)

7.9 Patient-reported outcome (PRO) assessments

At all in-clinic visits, all PRO assessments should be completed before other clinical assessments and procedures.

7.9.1 Worst itch numeric rating score (WI-NRS)

The subject's WI-NRS must be recorded by the subject in a diary once daily (at the same time of the day throughout the trial, i.e., morning, afternoon, or evening for all recordings) on day -7 to day 0 (where day 0 = next on-site visit day) leading up to each visit (8 days in total) at Baseline, Week 1, Week 4, Week 8, and Week 12 or Early Termination using an 11-point numeric rating scale ranging from 0 to 10:

Please score the intensity of the Worst Itch you have experienced in the past 24 hours: 0 (no itch), 1, 2, 3, 4, 5, 6, 7, 8, 9, 10 (very severe/extreme itch).

In addition, the subject's WI-NRS must be evaluated at on-site visits at Screening, Baseline, Week 1, Week 4, Week 8, and Week 12 or Early Termination using the 11-point verbal rating scale above.

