3.1 Primary Efficacy Endpoint

The primary efficacy endpoint is the mean change in weekly mean Worst Itch Numeric Rating Score (WI-NRS) recorded in the subject's diary from Baseline to Week 12 for MC2-25 cream compared to MC2-25 vehicle. Weekly mean WI-NRS is calculated as the average of all and at least 4 non-missing WI-NRS values recorded in the subjects' diaries for the 7 days prior to and including the scheduled in clinic visits (8 days in total expected). If less than 4 observations are recorded in the 8 days expected, the weekly mean WI-NRS will be considered missing.

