3.3 Secondary Efficacy Endpoints

The secondary efficacy endpoints will compare MC2-25 cream and MC2-25 vehicle for following points:

- Percentage of subjects obtaining a \geq 4-point improvement in weekly mean WI-NRS recorded in the subjects' diaries from Baseline to Week 1, Week 4 and Week 8.
- Percentage of subjects obtaining $a \ge 3$ -point improvement in weekly mean WI-NRS recorded in the subjects' diaries from Baseline to Week 1, Week 4, Week 8 and Week 12.
- Percentage of subjects obtaining a complete response in weekly WI-NRS recorded in the subjects' diaries from Baseline to Week 1, Week 4, Week 8 and Week 12. Complete response is defined as scores equal to 0 or 1 in \geq 80% of the non-missing WI-NRS values recorded in the subjects' diaries 7 days prior to and including the scheduled in clinic visits.
- Percentage of subjects obtaining an alternative complete response in weekly WI-NRS recorded in the subjects' diaries from Baseline to Week 1, Week 4, Week 8 and Week 12. Alternative complete response is defined as scores equal to 0 or 1 in ≥ 70% of the non-missing WI-NRS values recorded in the subjects' diaries 7 days prior to and including the scheduled in clinic visits.

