3.4 Other Efficacy Endpoints

Other endpoints compare MC2-25 cream and MC2-25 vehicle and are:

- Mean change in WI-NRS recorded in the subject's diary from Baseline to Week 1, Week 4, and Week 8.
- Mean change in WI-NRS recorded during on-site visits from Baseline to Week 1, Week 4, Week 8 and Week 12.
- Mean change in Sleeploss due to Itch Numeric Rating Score (SI-NRS) from Baseline to Week 1, Week 4, Week 8 and Week 12.
- Mean change in Skin Dryness Numeric Rating Score (SD-NRS) from Baseline to Week 1, Week 4, Week 8 and Week 12.

Table 2WI-NRS, SI-NRS, SD-NRS scale and scores:

Worst Itch/ Worst Sleep Loss/ Worst Skin Dryness in last 24 hours											
0	1	2	3	4	5	6	7	8	9	10	
No Itch/										Worst	
No										Imaginable	
Sleeploss/										Itch/	
No Skin										Sleeploss/	
Dryness										Skin	
-										Dryness	

- Percentage of subjects who reported an improvement in Subject's Global Impression of Change (SGIC) (i.e. "Very much better", "Much better" or "A little better") will be reported for Week 1, Week 4, Week 8 and Week 12 for WI-NRS, SI-NRS and SD-NRS.

Note: SGIC will be summarized for all subjects (see Table 3). Categories 1 to 3 will be summarized as combined "Improvement in SGIC score". Categories 1 to 7 will be summarized individually.

Table 3SGIC for itch, sleep loss and skin dryness.

Choose response that best describes overall change in itch, sleep loss and skin dryness since you started taking the trial medication.

since jou sur ou withing the true incurations							
Improvement in	1	Very much better					
SGIC	2	Much better					
(1 to 3)	3	A little better					
	4	No change					
	5	A little worse					
	6	Much worse					
	7	Very much worse					

- Percentage of subjects who reported "an important improvement" in Subject's rating of importance of improvement (i.e., subjects who respond "Yes" to Question 1 in the 'Subjects rating of importance' assessment) for WI, SI, and SD at Week 1, Week 4, Week 8, and Week 12 or ET.
- Mean change in Subject's indication of CKD-aP treatment area size from Baseline to Week 4, Week 8 and Week 12.
- Mean change in 5D-Itch (Domain Scores and Total Score) from Baseline to Week 4, Week 8 and Week 12

The 5D-Itch consists of 5 domains numbered 1-5.

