Baseline for efficacy and safety summaries is defined as the last observation prior to the first application of IMP except for weekly mean WI-NRS which is the average of at least 4 nonmissing WI-NRS values recorded in the subjects' diaries for the 7 days prior to and including the Baseline day. If there are less than 4 observations in the expected 8 days of entries, the baseline will be considered missing for weekly mean WI-NRS.

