5.2.3 Analysis Windows

As subjects do not always adhere to the protocol visit schedule, the following rules are applied to assign actual visits to analysis visits. Listed below are the visit windows and the target days for each visit. The reference day is Baseline, Study day 1. If a subject has 2 or more actual visits in 1 visit window, the visit closest to the target day will be used as the protocol visit for that visit window. The other additional visit(s) will not be used in the summaries or analyses, but they can be used for determination of clinically important endpoints. If 2 actual visits are equidistant from the target day within a visit window, the later visit is used.

Table 10 represents the analysis windows assigned for efficacy and safety analysis and the corresponding range of treatment days (window) during which data for a particular nominal visit will be collected. The analysis windows will be calculated from the first application of study product. These are analysis windows that contain, but are not same as, the actual visit windows.

For assessments that are not planned on Week 1, the visit window for such assessments will be starting at Week 4.

Study Week/ Period	Study Visit	Target Day	Window
Screening	Visit 1 (V1)	-28 to -1	
Baseline/ Week 0 (on site)	Visit 2 (V2)	1	1
Week 1 (on site)	Visit 3 (V3)	8 (±1)	2-19
Week 4 (on site)	Visit 5 (V5)	29 (±4)	20-43
Week 8 (on site)	Visit 7 (V7)	57 (±4)	44-71
Week 12 (on site/EoT)	Visit 9 (V9)	85 (±4)	72-92
Week 14 (FU)	Visit 10 (V10)	±2 Weeks after EoT	

Table 10Study Period, Visit and Target Day

For the hypothetical strategy, subjects given prohibited therapies will have WI-NRS data set to missing for visits after the start of the prohibited therapies and then missing data will be estimated using MIs. Subjects with an ET visit will be excluded from the PPS analyses. Safety data collected during an ET visit will remain at the Week 12/EoT visit.

Note: As per the CDISC, baseline is defined as Day 1 and not as Day 0. Therefore, there is a difference of one day between study day as defined in protocol and target day (Table 10).

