5.5.2 Secondary Efficacy Analyses

The key secondary and other secondary endpoints will be analyzed using a generalized estimating equations model with baseline weekly mean WI-NRS as a covariate and treatment,

MC2 Therapeutics Protocol No- MC2-25-C1 V3.0 SAP Final V1.0

CKD stage stratum at baseline, systemic CKP-aP treatment status at baseline and visit as fixed factors and subject as a random factor with a 2-sided $\alpha = 0.05$. An exchangeable covariance structure will be used. Estimates and SE for each treatment group will be displayed along with the difference in estimates between active and vehicle with the corresponding SE, 95% CI and p-value.

Descriptive summaries and listings by subject and visit will be provided.

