5.5.3 Other Efficacy Analyses

Descriptive summaries will be provided for all other efficacy endpoints by visit and treatment group. They will also be listed by subject and visit.

The mean change in weekly mean WI-NRS from baseline to Week 1, 4, and 8, respectively, will be analyzed like described for the primary efficacy analysis in Section 5.5.1.

The mean change in weekly mean WI-NRS will be assessed within treatment for both arms (MC2-25 cream and MC2-25 vehicle) for change from baseline for all visits i.e., Week 1, 4, 8 and 12 using a paired T-test.

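### At Week 1 the 8-day diary window reuses one or two Baseline itch scores, so Week 1 change is understated and responses are harder to reach by an amount that depends on the visit day

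*Protocol*

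**What the plan says.** **Diary window.** Protocol 7.9.1 asks for one score a day "on day -7 to day 0 (where day 0 = next on-site visit day) leading up to each visit (8 days in total"), and Table 3 footnote 6 repeats this. SAP 3.1 averages at least four entries "for the 7 days prior to and including the scheduled in clinic visits (8 days in total expected").

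**Baseline.** SAP 5.1 takes the entries "for the 7 days prior to and including the Baseline day", which agrees with inclusion criterion 6.

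**Week 1 timing.** Protocol Table 3 puts Week 1 at Day 7 ±1. The row in SAP Table 10 reads "Week 1 (on site) Visit 3 (V3) 8 (±1) 2-19". The SAP counts Baseline as Day 1, so its Day 8 is protocol Day 7. The range 2-19 assigns visits to time points; it does not redefine which daily scores enter a mean.

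**Use of Week 1.** All protocol efficacy endpoints are at Week 12. SAP 3.3 adds response rates at earlier visits: the 4-point item covers improvement "recorded in the subjects' diaries from Baseline to Week 1, Week 4 and Week 8", and the 3-point, complete and alternative complete response items also start at Week 1. SAP 3.4 adds "Mean change in WI-NRS recorded in the subject's diary from Baseline to Week 1, Week 4, and Week 8". These are modelled: SAP 5.5.2 states "The key secondary and other secondary endpoints will be analyzed using a generalized estimating equations model", and SAP 5.5.3 states "The mean change in weekly mean WI-NRS from baseline to Week 1, 4, and 8, respectively, will be analyzed like described" for the primary analysis, with paired t-tests within each arm as well.

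No passage in either document removes Baseline scores from the Week 1 mean.

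**The concern.** An 8-day window cannot fit into the 7 days between Baseline and an on-schedule Week 1 visit. The diary is kept once daily, so the overlap is the same entry counted twice, not two readings on one day. A score in both means contributes nothing to their difference, and the reported Week 1 change is pulled toward zero.

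The amount depends on whether the visit fell on Day 6, 7 or 8, all of which the protocol permits. Two subjects with identical itch histories can therefore be classified differently at Week 1. At stake are the Week 1 response rates and the size of the Week 1 mean change.

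**Working it through.** All days below use protocol numbering.

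**1. The plan's own figure.** Days -7 to 0 inclusive: 0 - (-7) + 1 = 8 days, as stated.

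**2. Overlap.** Baseline uses Days -7 to 0. A Week 1 visit on Day V uses Days V-7 to V.

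**3. Effect on change, complete diaries.** Let S be the sum of the shared scores, B the sum of the k non-shared Baseline scores, and L the sum of the k later scores, where k = 8 minus the number shared. Then

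improvement = (S + B)/8 - (S + L)/8 = (B - L)/8 = (k/8) × (mean of non-shared Baseline days - mean of later days).

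A 4-point response needs B - L ≥ 32, and a 3-point response needs B - L ≥ 24. Dividing by k gives the effective drop per day.

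| Visit day | Week 1 entries | Shared | k/8 | Drop needed, 4-point | Drop needed, 3-point |
|---|---|---|---|---|---|
| 6 | -1 to 6 | -1, 0 | 0.75 | 32/6 = 5.33 | 24/6 = 4.00 |
| 7 | 0 to 7 | 0 | 0.875 | 32/7 = 4.57 | 24/7 = 3.43 |
| 8 | 1 to 8 | none | 1 | 4.00 | 3.00 |

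**4. Example.** A subject scores 7 every day through Day 0 and 3 every day after. Week 1 improvement is 0.75 × 4 = 3.0 at Day 6, 0.875 × 4 = 3.5 at Day 7, and 4.0 at Day 8. Only the Day 8 visit gives a 4-point response.

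**5. Unreachable 4-point responses.** Inclusion criterion 6 admits Baseline means from 4. With 0 on every later day, L = 0 and B must still reach 32. So a 4-point response is impossible if the non-shared Baseline days average below 4.57 (Day 7) or 5.33 (Day 6). A subject constant at 5 through Day 0 and at 0 afterwards improves by 30/8 = 3.75 at Day 6 (not a response), 35/8 = 4.375 at Day 7 and 5.0 at Day 8 (both responses).

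**6. Complete response.** With 8 entries, the 80% rule needs 7 scores of 0 or 1 (0.8 × 8 = 6.4) and the 70% rule needs 6 (0.7 × 8 = 5.6).
- Day 6, both shared scores above 1: the most possible is 6/8 = 75%. The 80% rule cannot be met; the 70% rule can, if all six later scores qualify.
- Day 7, Day 0 score above 1: all seven later scores must qualify (7/8 = 87.5%), since 6/8 = 75% fails.

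**7. Later visits.** The earliest in-window Week 4 visit is Day 24, whose entries start on Day 17. Weeks 4, 8 and 12 share nothing with Baseline.

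**8. Incomplete diaries.** The factors in step 3 are then no longer exact. With only four entries and a flat Baseline, one shared plus three later entries gives 3/4, and two plus two gives 2/4.

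**The case against.** The strongest case against is that nothing here is miscalculated. The documents define an 8-day window and apply it consistently at every visit, so this is a choice of endpoint definition whose side effect appears at one early visit. The Week 1 response endpoints are SAP additions in an exploratory phase 2 trial with no multiplicity adjustment, and no decision is tied to them. That stands, and it sets the weight of the point.

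A reader might infer that the responder thresholds themselves have been raised. They have not: SAP 3.3 keeps 4 and 3 points. What rises is the drop required between non-shared days, and the exact figures need complete diaries.

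The unreachable 4-point response is partly a floor effect. A subject with a Baseline mean of exactly 4 needs 0 on every recorded day at any visit, including Week 12. The overlap adds only subjects somewhat above that floor who reach very low scores within a week.

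For mean change, if all visits fell on the same day and diaries were complete, the overlap would be a pure rescaling. Points of change would shrink, but the unadjusted standardised difference would not. The loss is therefore in the reported size of change, the fixed-threshold response rates, and the mixing of factors 0.75, 0.875 and 1 across visit days.

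**Conclusion.** The point holds as a minor one. As written, the plan understates Week 1 change by 12.5% at a Day 7 visit and 25% at a Day 6 visit, relative to the change between non-shared days and assuming complete diaries. It makes Week 1 response depend partly on visit timing. The documents give no expected split of Day 6, 7 and 8 visits, so the overall effect on the Week 1 response rates cannot be estimated.

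Two larger conclusions are not supported.
- **Favouring an arm.** The same rule applies to both arms, and nothing in the documents links visit day to treatment.
- **Distorting the Week 12 primary result.** Week 12 means share no days with Baseline. The model terms listed in SAP 5.5.1 include no treatment-by-visit interaction. If a single treatment effect were pooled over four equally weighted visits with a constant true effect, the overlap would shrink it to (0.875 + 3)/4 = 0.969 or (0.75 + 3)/4 = 0.938 of its value, about 3% or 6%. But the endpoint is defined at Week 12, and SAP 5.5.3 describes separate results for Weeks 1, 4 and 8. Pooling is one literal reading of the term list, not something the plan states.

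**What to change.** In SAP 3.1 and 3.3, state that for Week 1 the weekly mean and all responder definitions use only diary entries dated after the Baseline day (protocol Day 1, SAP Day 2, onward) within the 8-day window, with at least four non-missing entries. List this in SAP 6.2 as a change from Protocol 8.8.1. Leave Baseline and Weeks 4, 8 and 12 as they are. Shortening the window to 7 days ending on the visit day would not be enough, because a Day 6 visit would still share Day 0.

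No new data are needed: entries are already required on every day from Day 1 to an in-window Week 1 visit. The costs are:

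- **Fewer entries.** The Week 1 mean loses one entry at Day 7 and two at Day 6.
- **More missing values.** Some partial diaries go from valid to missing: those with at least four entries in total but at most three later ones. Assuming independent daily completion of 95%, 90%, 80% or 70% (not given in the documents), the binomial probability is 0.02%, 0.2%, 2.3% or 6.8% at Day 7 (one shared, seven later) and 0.2%, 1.5%, 8.9% or 19.8% at Day 6 (two shared, six later). An early end-of-treatment visit on Days 1-3 that is assigned to Week 1 has at most three later entries and would always be missing.
- **Per-protocol set.** SAP 5.2.1 describes this set both as multiply imputed, with its own seed, and as analysed as observed. How the new missing values are handled there depends on reconciling the two statements.
- **Primary-model inputs.** Week 1 values entering the repeated-measures model and the imputation change.
- **Complete response counts.** With a full diary at Day 6, 7 or 8, the 80% rule needs 5 of 6, 6 of 7 or 7 of 8, and the 70% rule needs 5 of 6, 5 of 7 or 6 of 8. The two rules coincide at a Day 6 visit. The four-entry minimum is also new for complete response.
- **What remains.** A Day 0 score recorded after the first application stays in Baseline, and the 24-hour recall of a Day 1 entry can still reach back before that application.
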